6 PROCEDURES

Any questions regarding the protocol should be directed to the Celgene Medical Monitor or designee. The procedures conducted for each subject enrolled in the study are outlined in Table 4 and Table 5 for Part A and Table 6 and Table 7 for Part B. All study visits will have $a \pm 2$ day window unless otherwise specified below or in the Table of Events. All laboratory blood samples should be drawn predose unless otherwise specified (eg, PK samples). For subjects enrolled on an alternate schedule (eg, D1-3/D8-10, D1-7, or D1-10 dosing schedules), please refer to Table of Events in Appendix K and Appendices M-O.

The study procedures should be recorded in the source document and the electronic case report forms (eCRF). In the event subjects fail Screening, minimal information will be documented on the eCRFs, per database instructions.

6.1 Screening Period

The Screening window starts 28 days prior to first dose of CC-90009. Refer to Table 4 – Table 7, this section, and Section 6.2 for detailed information on procedures performed and the schedule. For subjects enrolled on an alternate schedule (eg, D1-3/D8-10, D1-7, or D1-10), please refer to Table of Events in Appendix K and Appendices M-O.

Waivers to the protocol will not be granted during the conduct of this trial, under any circumstances.

Safety laboratory analyses will be performed locally. Screening laboratory values must demonstrate subject eligibility, but may be repeated within the screening window, if necessary.

The ICD will be administered at the Screening visit to all subjects by qualified study staff. It must be signed and dated by the subject and the administering staff prior to the start of any other study procedures and its completion documented in source documents and in the eCRF. All screening tests and procedures must be completed within 28 days prior to the first dose of CC-90009 according to the schedule shown in Table 4, Table 6, Table 31, Table 33, Table 35, and Table 37.

Adequate contraceptive methods as specified in the CC-90009 PPP (refer to Appendix L) must be used for at least 28 days before starting CC-90009, while participating in the study, during dose interruptions, and for at least 28 days for FCBP and 28 days for males after the last dose of CC-90009. The PPP applies to all subjects receiving CC-90009 therapy and will be given to sites as a separate document. Subjects will be counseled about appropriate contraception during Screening (refer to Section 6.1.1). Counseling should be documented in source documents.

The following will be performed at Screening, after signed informed consent has been obtained:

- Inclusion and exclusion criteria will be assessed at Screening and recorded in the source documents and the eCRF.
- Pregnancy prevention counseling (refer to Section 6.1.1).
- Medical (including surgical, COVID-19 vaccines, toxicities of prior treatments, known allergies) history, oncologic history, and demographic data (including each subject's date of birth, sex, race, and ethnicity) will be collected during Screening as consistent with local

regulations (eg, if the full date of birth will not be collected but only month and year, age at screening will be collected). Oncologic history will include a detailed history of the primary diagnosis and date, therapies, and responses.

- Information on prior and concomitant medications and procedures will be collected (refer to Section 6.2.1).
- Registration in the integrated response technology system (IRT).
- Adverse event monitoring (refer to Section 10).
- Height and weight measured.
- Vital signs assessed (refer to Section 6.2.3).
- Physical examination (source documented only) and ECOG PS (refer to Section 6.2.4).
- RT-PCR testing for SARS-CoV-2 is mandatory within 7 days prior to first dose of CC-90009 (C1D1). The RT-PCR test should be based on institutional or local guidelines.
- If a subject is identified to have SARS-CoV-2 infection during the screening period, subjects may be considered eligible for the study after meeting all inclusion/exclusion criteria related to active infection, and after meeting the following criteria:
 - At least 10 days (20 days for severe/critical illness) have passed since symptoms first appeared or positive RT-PCR or viral antigen test result, and
 - at least 24 hours have passed since last fever without the use of fever-reducing medications, and
 - acute symptoms (eg, cough, shortness of breath) have resolved, and
 - in the opinion of the investigator, there are no COVID-19 sequelae that may place the participant at a higher risk of receiving investigational treatment.
 - In the instance of a SARS-CoV-2 infection during Screening, the Screening period may be extended beyond the 28-day timeframe with Sponsor Medical Monitor approval; Any Screening tests already performed which could potentially be affected by the SARS-CoV-2 infection or its complications on an individual basis and agreed upon with the Sponsor Medical Monitor (eg, hematology and chemistry labs) should be repeated closer to C1D1.
- A 12-lead ECG in triplicate (refer to Section 6.2.5) will be performed ≥72 hours prior to the first dose of CC-90009 with results received from the central read prior to dosing to fulfill the eligibility criteria.
- Left Ventricular Ejection Fraction (LVEF) assessment (refer to Section 6.2.6).
- Pregnancy β-subunit of human chorionic gonadotropin (β-hCG) test for FCBP as per PPP (refer to Appendix L and Section 6.2.7).
 - As per the PPP, FCBP must have two negative pregnancy tests (sensitivity of at least 25 mIU/mL) prior to starting CC-90009. The first pregnancy test must be performed within 10-14 days prior to the start of CC-90009 and the second pregnancy test performed within 24 hours prior to the start of CC-90009. The results must be confirmed to be negative prior to dosing.
- Clinical laboratory tests [hematology, serum chemistry, glucose-6-phosphate dehydrogenase (G6PD), 25-hydroxyvitamin D level, PT, INR, PTT, and urinalysis; refer to Section 6.2.8] are

to be completed within the timeframe specified in Table 4, Table 6, Table 31, Table 33, Table 35, and Table 37.

- Both a free (ionized) serum calcium test and a corrected serum calcium test (corrected for albumin) should be obtained at Screening to establish baseline values; either may be used to fulfill the inclusion criteria (refer to Section 4.2).
- Creatinine clearance is determined at Screening.
- Disease (efficacy) assessments (refer to Section 6.4) with the bone marrow aspiration and/or biopsy are collected during Screening within 14 days (Day -14 through Day -1) prior to the first dose of CC-90009. Pharmacodynamic bone marrow biomarker samples are obtained at the same time (refer to Section 6.6.3).
 - In Part A, both bone marrow aspirate and biopsy are mandatory at all time points.
 - In Part B, both a bone marrow aspirate and biopsy should be performed at Screening. Thereafter, bone marrow aspirates are sufficient; a bone marrow biopsy can be collected in conjunction with an aspirate if it is standard institutional practice. A bone marrow biopsy must be collected if adequate aspirate sample is not attainable.
 - In Part B, bone marrow aspirate and/or biopsy, peripheral blood smear, and relevant clinical documentation will be sent to a central lab for analysis and to confirm diagnosis and baseline disease characteristics. Details on timing and quantity of material required will be specified in the laboratory manual. All hematology and bone marrow pathology reports generated by central laboratories and used to establish subject's eligibility will be sent for sponsor review ahead of cohort assignment (if timing allows based on clinical urgency) to provide for any deficiencies in documentation to be addressed.
 - In Part B, on a case-by-case basis and after consultation with the Medical Monitor, it will be determined if local pathology reports can be used to support R/R AML and R/R HR-MDS subjects' eligibility and cohort assignment. Please note that a bone marrow aspirate and/or biopsy sample is still required to be sent to the central laboratory prior to enrollment.
- Pharmacodynamic biomarker blood samples will be collected during Screening within 14 days (Day -14 through Day -1) prior to the first dose of CC-90009 (refer to Section 6.6.2). It is preferable to collect and process these samples on the same day that the bone marrow samples are obtained.
- Eligible subjects will start calcium, calcitriol, and vitamin D supplementation at least 3 days prior to the first dose of CC-90009 in Cycle 1 (refer to Section 7.2). Subjects will be provided with a diary card to record the date and time they take the supplements.

6.1.1 Pregnancy Risk Counseling

The CC-90009 PPP for Celgene Clinical Trials (refer to Appendix L) applies to all subjects receiving CC-90009 therapy and will be given to sites as a separate document.

Qualified healthcare professionals will be trained by Celgene, or designee, in the requirements specific to contraceptive counseling of subjects. Once trained these healthcare staff will counsel subjects prior to the administration of CC-90009 and at the beginning of each subsequent cycle to ensure that the subject has complied with all requirements including use of birth control and that the subject understands the risks associated with CC-90009. This step will be documented with a

completed Education and Counseling Guidance Document, and CC-90009 will not be administered until this step occurs.

Per the PPP, the Investigator must confirm with the subject at each visit that their methods of birth control follow the PPP or confirm the subject's commitment to complete abstinence.

A CC-90009 Information Sheet will be provided to each subject before the first dose of CC-90009.

6.2 Treatment Period

All subjects who fulfill the inclusion/exclusion criteria who are continuing in the study will be registered in the IRT system prior to receiving CC-90009 on Day 1 of Cycle 1.

All subjects will be required to start calcium, calcitriol, and vitamin D supplementation at least 3 days prior to the first dose of CC-90009 in each cycle and continue until \geq 3 days after the last dose of CC-90009 in each cycle (eg, \geq Day 8 when CC-90009 is administered on Days 1-5, \geq Day 10 when CC-90009 is administered on Days 1-7, or \geq Day 13 when CC-90009 is administered on Days 1-3/8-10 or Days 1-10). Supplementation may be extended if hypocalcemia occurs (refer to Section 7.2.13.2). Subjects will document taking the supplements on diary cards that will be reviewed on Day 1 of each cycle and at the EOT visit. Subjects should be adequately hydrated (eg, 2 to 3 liters of oral or IV fluids per day) starting the day prior to CC-90009 administration and continuing through each day of CC-90009 administration. Refer to Section 7.2 and Section 8.3 for detailed information.

6.2.1 Concomitant Medication and Procedures

All concomitant medications and procedures taken or conducted beginning when the subject signs the ICD, throughout the study, and until 28 days after the last dose of CC-90009 will be recorded in the source documents and eCRF.

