6.3 Follow-up Period

6.3.1 Safety Follow-up

All subjects will be followed for 28 days after the last dose of CC-90009 for AE reporting and concomitant medication information. The 28-day (\pm 3 days) safety follow-up contact may be by telephone. In addition, any SAEs made known to the Investigator at any time thereafter that are suspected of being related to CC-90009 will be reported as described in Section 10.1. Subjects will be followed for all SAEs and all AEs (SAEs and non-serious AEs) associated with confirmed or suspected SARS-CoV-2 infection until resolution, the condition stabilizes, the event is otherwise explained, the event is deemed irreversible, the subject is lost to follow-up, or for suspected cases, until SARS-CoV-2 infection is ruled-out.

Pregnancy testing will be performed per the PPP and Table 5, Table 7, Table 32, Table 34, Table 36, or Table 38.

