6.3.2 Efficacy Long Term Follow-up

Subjects without documented progression of disease (or relapse) or start of new anti-cancer therapies will have efficacy evaluations of complete blood counts and peripheral blood smears performed every subsequent 8 weeks (± 1 week) for the 1st year and every 12 weeks (± 2 weeks) for the 2nd year or until progression of disease (or relapse), initiation of a new anticancer therapy, withdrawal from the study, death, or the End of Trial, whichever comes first. A bone marrow evaluation will be completed at the end of the 1st year and as clinically indicated during the Follow-up Period.

Information (including dates) on new anticancer therapies initiated will be collected until progression of disease (or relapse), withdrawal from the study, death, or the End of Trial, whichever comes first.

Information will also be collected on any study drug-related SAEs.

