7.2.13.3 Neutropenia and Anemia

Hematopoietic growth factors or other hematologic support, such as erythropoietin, darbepoetin, granulocyte-colony stimulating factor (G-CSF), granulocyte-macrophage colony stimulating factor, RBC- or platelet- transfusions are allowed in the study with therapeutic intent. Therapeutic use of G-CSF is allowed at any time for subjects experiencing Grade 3/4 neutropenia or any grade febrile neutropenia. Prophylactic use of granulocyte (or granulocyte-macrophage) growth factors is not allowed during Cycle 1.

Subjects with Grade 3 or 4 neutropenia should be monitored frequently with laboratory tests until resolution to Grade ≤ 1 . Antimicrobial, antifungal, and antiviral prophylaxis should be considered and provided per institutional standard medical practice.

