8 CONCOMITANT MEDICATIONS AND PROCEDURES

All medications (excluding prior cancer therapy for the tumor under evaluation) taken beginning when the subject signs the ICD and all concomitant therapy during the study until 28 days after treatment discontinuation, together with dose, dose frequency and reasons for therapy use will be documented in the source documents and on the concomitant medication eCRF.

All prior cancer therapy for the tumor under evaluation, including chemotherapy, biologic, immunologic, irradiation, and surgery, will be documented on dedicated prior cancer treatment eCRFs.

The Investigator will instruct subjects to notify the study staff about any new medications taken after signing the ICD. All medications and significant non-drug therapies (herbal medicines, physical therapy, etc.) and any changes in dosing with existing medications will be documented on the eCRFs.

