Appendix F: International Working Group (IWG) Response Criteria for Myelodysplasia

	Table 21:	Modified IWG Response	Criteria for MDS
--	-----------	------------------------------	------------------

Category	Response criteria (responses must last at least 4 weeks)
Complete remission (CR)	Bone marrow: \leq 5% myeloblasts with normal maturation of all cell lines ^a
	Persistent dysplasia will be noted ^{a,b}
	Peripheral blood ^c
	- Hemoglobin $\geq 11 \text{ g/dL}$
	- Platelets $\geq 100 \times 10^9/L$
	- Neutrophils $\geq 1.0 \times 10^9/L^b$ - Blasts 0%
Partial remission (PR)	All CR criteria if abnormal before treatment, except:
Fartial Tellission (FK)	Bone marrow blasts decreased by $\geq 50\%$ over pretreatment but still $> 5\%$
	Cellularity and morphology not relevant
Marrow CR ^b	Bone marrow: $\leq 5\%$ myeloblasts and decrease by $\geq 50\%$ over pretreatment ^b
± Hematologic Improvement	Note: Blasts at baseline must be $\geq 5\%$ in order for subject to be evaluable for
(HI)	Marrow CR ^d
()	Peripheral blood: if HI responses, they will be noted in addition to marrow CR ^b
Stable disease (SD)	Failure to achieve at least PR, but no evidence of progression for > 8 weeks
Failure	Death during treatment or disease progression characterized by worsening of
	cytopenias, increase in percentage of bone marrow blasts, or progression to a
	more advanced MDS FAB subtype than pretreatment
Relapse after CR or PR	At least 1 of the following:
	• Return to pretreatment bone marrow blast percentage
	• Decrement of \geq 50% from maximum remission/response levels in
	granulocytes or platelets
	• Reduction of Hgb concentration by ≥ 1.5 g/dL or transfusion dependence
Cytogenetic Response	Complete – Disappearance of the chromosomal abnormality without
e juegenene reeponee	appearance of new ones
	Partial – At least 50% reduction of the chromosomal abnormality
Disease Progression (PD)	For patients with:
	• Less than 5% blasts: \geq 50% increase in blasts to > 5% blasts
	• 5% - 10% blasts: \geq 50% increase in blasts to $>$ 10% blasts
	• $10\% - 20\%$ blasts: $\ge 50\%$ increase in blasts to $> 20\%$ blasts
	Any of the following:
	• At least 50% decrement from maximum remission/response levels in
	granulocytes or platelets
	• Reduction in Hgb concentration by $\geq 2 \text{ g/dL}$
	Transfusion dependence
Disease transformation	Transformation to AML (20% or more BM or PB blasts) ^d
Hematologic Improvement (HI)	
Erythroid response (HI-E)	Hgb increase by ≥ 1.5 g/dL

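### In HR-MDS, the transfusion criterion for relapse cannot be ascertained from the planned data more than 28 days after the last dose, so off-treatment response durations and RFS run long for some responders

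*Combined protocol and SAP*

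**What the plan says.** **Criteria.** Table 21 defines HR-MDS relapse after CR or PR by any one of several findings. One of them reads "Reduction of Hgb concentration by ≥ 1.5 g/dL or transfusion dependence". Transfusion dependence is also listed under disease progression in the same table. Section 2 names RFS, PFS, duration of remission and duration of response as secondary HR-MDS endpoints, assessed through the Follow-up Period.

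**Transfusions.** Section 7.2.13.3 states that "RBC- or platelet- transfusions are allowed in the study with therapeutic intent". No separate transfusion record is described, so they would be captured as concomitant procedures. Under Section 6.2.1 those are recorded from consent, "throughout the study, and until 28 days after the last dose of CC-90009 will be recorded in the source documents and eCRF". Section 6.3.1 says "All subjects will be followed for 28 days after the last dose of CC-90009 for AE reporting and concomitant medication information", and Section 8 covers "all concomitant therapy during the study until 28 days after treatment discontinuation".

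**Off treatment.** Section 6.3.2 plans "efficacy evaluations of complete blood counts and peripheral blood smears performed every subsequent 8 weeks" in the first year and 12-weekly in the second. It adds a marrow at the end of year 1 and otherwise when clinically indicated, new anticancer therapies, and drug-related SAEs. Transfusions are not on that list. In Table 36 the last concomitant-procedure entry is the Safety visit. The follow-up rows include an HR-MDS item for transformation to AML, but none for transfusions.

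**The concern.** One of the listed ways for an HR-MDS responder to relapse has no data behind it once the 28-day window closes. The gap also reaches two neighbouring criteria. A red-cell transfusion can hold haemoglobin above the relapse threshold, and a platelet transfusion can do the same for platelets, and an analyst who cannot see the transfusion cannot tell.

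The error runs one way. A responder who starts to need transfusions after stopping treatment may still be counted as in remission, or be dated as relapsing later, when another criterion is met. Durations are then overstated. The SAP can set event and censoring rules, but it cannot apply a transfusion rule to a dataset without transfusion dates and units.

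**Working it through.** No sample size or power figure depends on this, and the plan gives no figure to reproduce. The check compares criteria with data, then counts visits.

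**Step 1. Each Table 21 relapse criterion against what is planned more than 28 days after the last dose** (Sections 6.2.8 and 6.3.2):

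| Criterion | Planned data | Assessable? |
|---|---|---|
| Marrow blasts back to pretreatment level | Marrow at end of year 1 or when clinically indicated | Yes, at those times |
| Granulocytes down at least 50% | Differential at each visit | Yes |
| Platelets down at least 50% | Platelet count at each visit | Yes, but transfusion support unknown |
| Haemoglobin down at least 1.5 g/dL | Haemoglobin at each visit | Yes, but transfusion support unknown |
| Transfusion dependence | None | No |

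The Table 21 progression list (blast increase, count falls, haemoglobin fall of at least 2 g/dL, transfusion dependence) shows the same pattern.

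**Step 2. Is 28 days the right reading?** The reference in Section 6.2.1 to the whole study could suggest longer recording. Sections 6.3.1 and 8 and the empty long-term column of Table 36 all support the 28-day reading.

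**Step 3. How much of the look-back is recorded?** Table 22 defines red-cell dependence as at least 4 units in the previous 56 days, but only at screening. Its on-treatment cell for dependence is empty, and it gives no off-treatment definition. Taking 56 days as an assumption:

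- Scheduled visits: 365/56 gives 6 in year 1 and 365/84 gives 4 in year 2, so about 10.
- Counted from the 28-day safety visit, visits fall on days 84, 140, 196, 252, 308, 364, 477, 561, 645 and 729 after the last dose. The first look-back runs from day 84 − 56 = 28, which is where recording ends. Visits with any recorded look-back: 0 of 10.
- Counted from the last dose, the first visit is day 56, with 28 of its 56 look-back days recorded. The second is day 112, with a look-back starting at day 56, so no overlap. Visits with a complete look-back: 0 of 10.
- Share of two years from the last dose with no planned transfusion record: (730 − 28)/730 = 702/730 = 96%.

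**Step 4. Which endpoints?** Duration of remission or response and RFS depend on relapse, and for HR-MDS Table 21 is the relapse definition (Table 18 covers AML). PFS is less clear. Section 6.4 defines progression by marrow or peripheral blasts alone, in wording not restricted to AML, and Section 3.1 points to Section 6.4 for progression. If that definition governs HR-MDS, transfusion data do not enter PFS. If Table 21 governs, they do.

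**The case against.** The strongest reply is that the Table 21 criteria are alternatives and most of them survive. Counts continue every 8 to 12 weeks, red-cell transfusion does not hide a fall in granulocytes, and marrow can be done when clinically indicated. New transfusion need might itself prompt a marrow, and an investigator may use the medical record when judging relapse. All of this stands, and it rules out several stronger readings:

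- A reader might infer that these endpoints cannot be determined at all off treatment, or that haemoglobin is lost. Neither follows, because haemoglobin is measured at every visit and relapse can still be established by other criteria.
- A reader might infer that every HR-MDS responder is affected. Only those whose first sign is transfusion need or a masked count are misdated. Section 3.1 also allows benefiting subjects to continue beyond Cycle 4, with transfusions still recorded, whereas Section 7.2 gives a maximum of 4 cycles. Those passages must be reconciled, and off-treatment response time depends on the outcome.
- A reader might infer that the information is lost for good. It may still be in hospital records; it is simply absent from the planned dataset.

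It is also fair that the study is Phase 1, that analyses are descriptive, and that the efficacy variables of main interest, ORR and CRR, are rates rather than durations. No stopping rule or sample size depends on this point. What the reply does not answer is the missing criterion: no section provides for recording transfusions in efficacy follow-up.

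**Conclusion.** The point holds as one of incomplete ascertainment. More than 28 days after the last dose, transfusion dependence cannot be ascertained from the planned data, and haemoglobin and platelets cannot be read against transfusion support. Off-treatment duration of remission or response and RFS in HR-MDS are biased long for the responders described.

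Size: no scheduled off-treatment visit has a complete look-back, but the number of subjects misdated cannot be estimated from the documents. Up to 20 HR-MDS subjects in each of the two new dose cohorts, 40 in all, is a ceiling on enrolment, not a count of affected responders.

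The conclusion assumes that transfusions are captured only as concomitant procedures. The visit counts assume the screening look-back of 56 days. An unqualified claim about PFS is not supported, because the governing progression definition is unsettled. Nor can it be assumed that every Table 21 criterion will count as an endpoint event, since Section 9.6.2 leaves the full analysis details to the SAP and the combined document gives no event or censoring rules for these endpoints. This is a worthwhile, inexpensive improvement to secondary descriptive endpoints.

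**What to change.** 1. In Section 6.3.2 and the long-term column of Table 36 (and Table 7 for any HR-MDS subject still followed on that schedule), record red-cell and platelet transfusions since the last contact at each scheduled 8- or 12-week visit, for HR-MDS subjects in efficacy follow-up. Capture date, units, and pre-transfusion haemoglobin or platelets where available. The pre-transfusion haemoglobin matters because Table 22 counts red-cell transfusions in its on-treatment response evaluation only when given at 9.0 g/dL or below.
2. Exempt these records from the 28-day limit in Sections 6.2.1 and 8, and align Section 6.3.1.
3. State the look-back that defines transfusion dependence off treatment.
4. Reconcile the Section 6.4 and Table 21 progression definitions for HR-MDS, and say which one PFS uses.

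If the sponsor prefers not to collect transfusions, the minimum is to state that off-treatment HR-MDS events rest on counts and blasts only, and to report the durations with that limitation.

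Cost: one eCRF page at visits already planned, with a small amount of site data entry. No new procedure is needed.
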